#### 10.3.1 Datasets to be Analyzed, Analysis Populations

All Study participants that terminated the study (n = max 20 volunteers)

#### 10.3.2 Primary Analysis

Descriptive comparisons of microbiological data before and after PDT by [name]

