## 2.5 Explanation for Choice of Comparator Intervention

We will use for our control group without PDT the contralateral groin of the same participants (no further participants needed).

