### **3.2 Primary Objective**

In this study we aim to investigate if PDT with MAL or methylene blue has an effect on bacterial skin colonization and decreases number of colonizing bacteria to improve skin antisepsis strategies for the prevention of surgical site infections.

In a previous pilot study, we investigated if skin antisepsis can be improved with previous PDT with MAL-induced Pp IX on inguinal skin in 10 participants. We showed a complete sterilization of colonizing skin bacteria at the same day after this treatment. However, orthopedic surgeons are hesitant to perform an arthroplastic surgery after such a treatment due to skin erythema for a few days.

We are entirely convinced about this novel prevention concept but need to identify the optimal irradiation source and the photosensitizer with the ideal balance of antibacterial effect versus skin irritation.

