## **4 STUDY OUTCOMES**

### **4.1 Primary Outcome**

Effect of PDT with the MAL-induced Pp IX (group A) and Methylene blue (Ondine NF-031) (group B) in combination with skin antisepsis on bacterial skin colonization on the day of application and on day 0, 1, 3 and 5

- 1.1. To quantitatively evaluate bacterial density and species before and after PDT and skin antisepsis using culture techniques

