## Microbiology

In short, the patient's sample swabs will be streaked out onto Columbia sheep blood agar plate without antibiotics (bioMérieux, Marly-l'Etoile, France), colistin-nalidixic acid (CNA) blood agar (bioMérieux) plate for aerobic cultivation and a Brucella plate (in-house sheep blood agar plates with hemin and vitamin K1) for anaerobic cultivation using GENbag (bioMérieux). Final identification will be done by matrix-assisted laser desorption ionization-time of flight mass spectrometry spectrometry (MALDI-TOF MS) using a Bruker MALDI Biotyper. The amount of bacteria will be semiquantitative described as +, ++, +++ based on growth on agar plates. All cultured microorganisms will be stored in skim milk at -80C° for potential subsequent analysis by whole genome sequencing for analyzing the secondary outcome.

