### 10.1 Hypothesis

We hypothesize that PDT improves skin antisepsis by reduction of persistent skin colonizing bacteria by its bactericidal effects.

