### 10.3 Planned Analyses

- As a pilot study, we plan to do descriptive statistics only.
- Categorical data will be tested for differences using Fisher's exact or chi-squared tests.
- Continuous variables will be tested using Wilcoxon rank sum tests.
- Data will be analyzed using Stata® version 14.2 (Stata Corporation, College Station, TX). Two-tailed P-values <0.05 are considered statistically significant.

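### The primary analysis compares only before and after PDT and never uses the antisepsis-only contralateral groin, so it cannot show that PDT adds to antisepsis

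*Combined protocol and SAP*

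**What the plan says.** - **Hypothesis (10.1):** "We hypothesize that PDT improves skin antisepsis by reduction of persistent skin colonizing bacteria by its bactericidal effects". This concerns an increment over antisepsis.
- **Objective (3.2):** whether PDT with either agent "has an effect on bacterial skin colonization and decreases number of colonizing bacteria to improve skin antisepsis strategies".
- **Outcome (4.1):** "To quantitatively evaluate bacterial density and species before and after PDT and skin antisepsis using culture techniques", on days 0, 1, 3 and 5. Under Microbiology in 8.2.1: "The amount of bacteria will be semiquantitative described as +, ++, +++ based on growth on agar plates".
- **Comparator (2.5):** "We will use for our control group without PDT the contralateral groin of the same participants". The synopsis, 5.2 and 7.1.2 also describe this control.
- **Primary analysis (10.3.2):** "Descriptive comparisons of microbiological data before and after PDT". No part of section 10 refers to the contralateral groin or to antisepsis alone.
- **Tests (10.3):** "As a pilot study, we plan to do descriptive statistics only", followed by Fisher or chi-squared tests for categorical data and "Continuous variables will be tested using Wilcoxon rank sum tests", two-tailed at 0.05. The groups to be compared are not named.
- **Control coverage:** all participants in 5.2, 10 participants in the synopsis, the first 10 in 7.1.2. By 2.7 the first 10 enrolled are all group A (MAL).
- **Day-0 sampling:** 7.2.1 and the table in 8.1 list a scraping between PDT and antisepsis. The narratives in 5.2 and 8.3.2 put antisepsis straight after PDT and name no scraping in between.

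**The concern.** The antisepsis-only groin is collected but given no role in the analysis. What is planned instead is a before/after contrast in the treated groin, which has two possible meanings, and neither answers 10.1.

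If the after sample is post-antisepsis, it mixes the effects of PDT and of the antiseptic, so PDT that adds nothing still appears to work. If it is post-PDT and pre-antisepsis, a real fall may add nothing once the antiseptic is applied.

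The pilot is meant to decide whether a hip arthroplasty trial follows. Section 2.4 ties that decision to sterile cultures after PDT and antisepsis, again without reference to a control.

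The tests listed in 10.3 are for independent groups, while the two groins belong to one person.

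Under 5.2 the control swabs would exist and the contrast could be computed, but no analysis of them is specified. Under 7.1.2 the methylene blue arm would have no within-person control, and swabs never taken cannot be recovered.

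**Working it through.** The plan gives no effect size, culture-positive rate or power, so it has no figure to reproduce. The calculations below only illustrate the size of the problem.

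**Inputs.** From the plan: n = 10 per arm, two-sided 0.05. Assumed, not in the documents: growth yes/no as the endpoint; baseline positivity π = 100, 80 or 60%; antisepsis clears a share p = 30, 50 or 70% of positive groins; PDT is inert; the after sample is post-antisepsis; the two groins of a participant are independent given the rates.

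**Before/after in the PDT groin.** Expected fall = 100·π·p points. The number of groins turning negative is Bin(10, π·p). For π = 1 and p = 0.5, P(at least 3) = 1 − (1 + 10 + 45)/1024 = 0.945.

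**PDT versus contralateral groin, both after antisepsis.** Each side is Bin(10, q) with q = π(1 − p), so the expected difference is 0. For exact McNemar each discordant cell has probability q(1 − q).

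Entries are for p = 30/50/70%:

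| Baseline positive | Expected before/after fall (points) | P(fall ≥ 3 of 10) | P(contralateral difference ≥ 3 of 10 favouring PDT) | Fisher p<0.05 on before/after | McNemar p<0.05 on contralateral contrast |
|---|---|---|---|---|---|
| 100% | 30/50/70 | 62/95/>99% | 11/13/11% | 15/62/95% | 0.5/0.9/0.5% |
| 80% | 24/40/56 | 44/83/98% | 13/13/9% | 3/19/55% | 0.9/0.8/0.3% |
| 60% | 18/30/42 | 26/62/86% | 13/11/7% | 0.5/6/24% | 0.8/0.5/0.1% |

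The last two columns change both test and contrast, so they do not compare Fisher with McNemar. With exact McNemar on before/after as well (π = 1), p<0.05 occurs in 5/38/85% of trials: the contrast, not the test, drives the result.

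**Precision of the contralateral contrast.** With 0 of 10 positive on the PDT side and 3, 5 or 7 of 10 on the control side, the difference is 30, 50 or 70 points. Tango score 95% CIs are −6 to 60, 8 to 76 and 23 to 89.

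**Power of the contralateral contrast.** With k discordant pairs all in one direction, the two-sided McNemar p is 2 × 0.5^k: 0.0625 for k = 5 and 0.031 for k = 6. If the PDT side is always sterile and a share q of control groins stays positive, power = P(Bin(10, q) ≥ 6) = 5/38/85% for q = 30/50/70%.

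**The case against.** The strongest reply is that this is an open-label descriptive pilot and that 10.3.2 matches the before/after wording of 4.1 and much of 3.2, so the mismatch is with 10.1 only. The comparator is declared in several places, and the tests in 10.3 name no groups, so a comparison with the control groin is not excluded. The partial match stands. But a descriptive analysis still has to describe the contrast that bears on the hypothesis, and the plan never links comparator to analysis.

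Second, the inert-PDT figures depend on reading the after sample as post-antisepsis. That is correct. On the other reading the antiseptic does not contaminate the contrast and the table does not apply. What remains is that PDT alone does not show an increment over antisepsis, and whether that sample is taken on day 0 is itself inconsistent.

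Third, with independent groins Fisher is valid for the contralateral contrast (at most 1.3% false positives across the nine scenarios) and more powerful than exact McNemar (15/62/95% against 5/38/85% in the power scenario above). This also stands, under that assumption. Paired methods remain the standard for two sites on one person, but no inflated error from Fisher is shown here, and the main request is an interval.

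Fourth, permanent loss of group B controls comes from 7.1.2 conflicting with 5.2, not from 10.3.2. That is true, but the contrast needed in 10.3.2 depends on those swabs, so the two should be settled together.

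**Conclusion.** The concern holds. As written, the primary analysis cannot attribute a fall in colonization to PDT over antisepsis under either reading of the after sample. This follows from the text and needs no assumed rate.

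The size is illustrative. Under the post-antisepsis reading, inert PDT would produce an expected apparent fall of 18 to 70 points across the scenarios, against an expected contralateral difference of 0. The gap narrows as baseline positivity or clearance falls. The clearance rates, the baseline rates and the independence of groins are all assumptions.

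The omission in 10.3.2 can be repaired while the swabs exist. If 7.1.2 is followed, the group B comparison is lost for good.

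**What to change.** 1. In 10.3.2 state, for each arm, the within-participant difference between PDT groin and contralateral groin in day-0 post-antisepsis growth. Give semiquantitative grade and growth yes/no, as an estimate with 95% CI. Describe species and report baseline swabs of both sides.
2. If this contrast is tested, use paired methods (sign or signed-rank for grade, exact McNemar for growth) in place of rank sum and Fisher, and reconcile any testing with the descriptive-only statement in 10.3.
3. Keep before/after PDT, on the pre-antisepsis scraping, as the effect of PDT alone. Keep days 1, 3 and 5 in the primary outcome as 4.1 has them, and state on which days the control groin is sampled.
4. Reconcile control coverage between 5.2, the synopsis and 7.1.2 so that both arms have day-0 contralateral samples.
5. Align the day-0 narratives in 5.2 and 8.3.2 with 7.2.1 and the table in 8.1 on the scraping between PDT and antisepsis.

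**Cost.** A protocol amendment with ethics approval, since 1.14 counts a changed form of statistical analysis as substantial; it should be made before enrolment starts. Control scrapings in 20 participants are what 5.2 already plans, but 10 more than 7.1.2. The apparent effect is likely to be smaller than a before/after fall. With 10 pairs per arm the result should be read as an estimate, not a confirmatory test.

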#### 10.3.3 Secondary Analyses

Statistical analysis of microbiological data using whole-genome analysis: will be done by [name] in collaboration with the Institute of Medical Microbiology and the Clinic for Dermatology.

These analysis will be done after termination of all study participants

#### 10.3.4 Interim Analyses

No interim analyses is needed for this small study design.

#### 10.3.5 Safety Analysis

Analysis of SAE as standard (number of adverse and serious adverse events)

#### 10.3.6 Deviation(s) from the Original Statistical Plan

Not applicable.

### 10.4 Handling of Missing Data and Drop-Outs

Missing outcome data will be handled as missing. No imputation methods will be used.

## **12 DATA QUALITY ASSURANCE AND CONTROL**

The Sponsor-Investigator is implementing and maintaining quality assurance and quality control systems with written SOPs and Working Instructions to ensure that trials are conducted and data are generated, documented (record), and reported in compliance with the protocol, GCP, and applicable regulatory requirement(s).

### **12.1 DATA HANDLING AND RECORD KEEPING**

The study will strictly follow the protocol. If any changes become necessary, they must be laid down in an amendment to the protocol. All amendments of the protocol must be signed by the Sponsor-Investigator and if essential submitted to CEC.

#### **12.1.1 Case Report Forms**

The investigators will use electronic case report forms eCRF, one for each enrolled study participant, to be filled in with all relevant data pertaining to the participant during the study. All participants who either entered the study or were considered not-eligible or were eligible but not enrolled into the study additionally have to be documented on a screening log. The investigator will document the participation of each study participant on the Enrolment Log.

##### For studies with electronic CRF:

For data and query management, monitoring, reporting and coding an internet-based secure data base Redcap® developed in agreement to the Good Clinical Practice (GCP) guidelines will be used for this study. It is the responsibility of the investigator to assure that all data in the course of the study will be entered completely and correctly in the respective data base. Corrections in the eCRF may only be done by the investigator or by other authorized persons. In case of corrections the original data entries will be archived in the system and can be made visible. For all data entries and corrections date, time of day and person who is performing the entries will be generated automatically.

CRFs/eCRFs will be kept current to reflect participant status at each phase during the course of study. Participants must not to be identified in the eCRF by name. Appropriate coded identification (e.g. Participant Number) will be used.

We assure that any authorized person, who may perform data entries and changes in the eCRF, can be identified. A list with signatures and initials of all authorized persons will be filed in the study site file and the trial master file, respectively.

The investigators assure to perform a complete and accurate documentation of the participant data in the eCRF. All data entered into the eCRF must also be available in the individual participant file either as print-outs or as notes taken by either the investigator or another responsible person assigned by the investigator.

Essential documents must be retained for at least 10 years after the regular end or a premature termination of the respective study (KlinV Art. 45).

Any patient files and source data will be archived for the longest possible period of time according to the feasibility of the investigational site, e.g. hospital, institution or private practice.

### **12.1.2 Specification of Source Documents**

The following documents are considered source data, including but not limited to:

- SAE worksheets
- Nurse records, records of clinical coordinators, and

Source data must be available at the site to document the existence of the study participants and substantiate the integrity of study data collected. Source data must include the original documents relating to the study, as well as the medical treatment and medical history of the participant.

The following information (at least but not limited to) should be included in the source documents:

- Demographic data (age, sex)
- Inclusion and Exclusion Criteria details
- Participation in study and signed and dated Informed Consent Forms
- Visit dates
- Microbiological data (identification of bacteria)
- Side effects of PDT (pain, redness)
- SAEs (related) and concomitant medication
- Reason for premature discontinuation

### **12.1.3 Record Keeping / Archiving**

All study data will be archived for a minimum of 10 years after study termination or premature termination of the clinical trial (at the Division of Infectious Diseases, University Hospital Zurich).

## **12.2 Data Management**

All basic demographic data, all microbiological and histopathological results will be manually entered in an automatically secured online processing system (REDCap® electronic data capture system). The PI will check and validate data on a regular basis for consistency.

All study data are encrypted in REDCap®. The principal investigator is responsible for data collection and will keep the screening log, which guarantees the confidentiality of data by the use of participant ID numbers. The participant ID numbers are automatically assigned in consecutive ascending form by the REDCap® system. For the purpose of fulfilling their task, the principal investigator grants the necessary access authorization in the form of user log-in and password to the study staff. Thus, the data cannot be altered in any way by unauthorized persons. In the REDCap® system, all relevant processing operations are documented in a user-specific manner in order to ensure traceability. This is done by means of registration software, which records who has edited which data at which time.

All patients have to give their written consent to the project. These informed consents documents (IC) will be stored according to ethical regulations.

Health related personal data captured during this project from participants are strictly confidential and disclosure to third parties is prohibited; coding will safeguard participants' confidentiality. Confidentiality will be ensured by using coded data. The code will be protected against unauthorized access and will be stored appropriately. Data will be stored for up to 10 years after publishing the study as requested by most journals.

- Patient's and microbiological data:

- [name] will be responsible for basic characteristics of the volunteers of this pilot study. After the last study visit, data will be encoded by the PI and safely stored at the Investigator Site File.
- Clinical and microbiological data will be saved in the electronical database Redcap (see above)
- The collected project data may be subject to inspection by the CEC.

- *Handling of isolated bacteria of the scrapped skin samples:*  
The sub-cultivated bacterial samples will be stored and labeled with an encoded name at -80°C at the bacteriology laboratory of the Division of Infectious Diseases and Hospital Epidemiology (responsible [name]). The code for the bacterial strains with correspondence to patient data will be stored at the Investigator Site File.

### **12.3 Routine Monitoring**

Since we only measure microbiological data from skin samples, we think, that an interne monitoring would be adequate. This would include:

- Microbiological study part (cultivation procedures) under supervision of [name]. Regular control of study result by a microbiologist not involved in the study (to be determined)
- Data entry will be done by a doctorand or research associate and by the study nurse by a 4-eyes control. Control of data entry, informed consents, and SAE will be done by the sponsor and by [name] (attending physician of the Division of Infectious Diseases and Hospital Epidemiology) on a regular base (4-eyes principle).

### **12.4 Audits and Inspections**

A quality assurance audit/inspection of this study may be conducted by the CEC. The quality assurance auditor/inspector will have access to all medical records, the investigator's study related files and correspondence, and the informed consent documentation that is relevant to this clinical study.

The investigator will allow the persons being responsible for the audit or the inspection to have access to the source data/documents and to answer any questions arising. All involved parties will keep the patient data strictly confidential.

### **12.5 Confidentiality, Data Protection**

Direct access to source documents will be permitted for purposes of monitoring, audits and inspections.

### **12.6 Storage of Biological Material and Related Health Data**

Encoded data will be stored for up to 10 years after publishing the study as requested by most journals.

The biological material will be labeled with an encoded name and stored at -80°C at the Division of Infectious Diseases and Hospital Epidemiology by the end of the study and destroyed after the end of the study. With the second signature in the study informed consent, further use of data [and the biological material for other research projects is possible](#).

## **13 PUBLICATION AND DISSEMINATION POLICY**

After the statistical analysis of this trial the sponsor will make every endeavor to publish the data in a medical journal.

Data of this study can only be published if [name], [name] and [name] agree on the data presentation, analysis, and authors list.

☞ **Commitment for study coordination, ethical protocol, generate microbiological data, data entry, study analysis:** Division of Infectious Diseases and Hospital Epidemiology, USZ ([name])

☞ **Commitment for PDT application:** Clinic for Dermatology, University Hospital of Zurich ([name])

☞ **Commitment for bacterial culture, bacterial identification, storage:** Institut of Medical Microbiology, UZH ([name])

The Principal Investigator will perform the study in accordance with the current protocol version. The Principal Investigator will ensure that any investigators and any other staff comply with the terms of the Protocol and this agreement.

## 14 FUNDING AND SUPPORT

### 14.1 Funding

This study is financed by the sponsor and PI ([name])

External funding is provided by the Vontobel foundation. The company Galderma and Ondine company will provide the photosensitizers.

### 14.2 Other Support

## 15 INSURANCE

Insurance is covered by "Versicherung für klinische Versuche und nichtklinische Versuche" by Zürich Versicherungs-Gesellschaft AG (Policy no.: 14.970.888).

Any damage developed in relation to study participation is covered by this insurance. So as not to forfeit their insurance cover, the participants themselves must strictly follow the instructions of the study personnel. Participants must not be involved in any other medical treatment without permission of the principal investigator (emergency excluded). Medical emergency treatment must be reported immediately to the investigator. The investigator must also be informed instantly, in the event of health problems or other damages during or after the course of study treatment.

The investigator will allow delegates of the insurance company to have access to the source data/documents as necessary to clarify a case of damage related to study participation. All involved parties will keep the patient data strictly confidential.

A copy of the insurance certificate will be placed in the Investigator's Site File.

## 17 APPENDICES

### ***Appendix 1: Documentation of PDT (example for MAL PDT)***

Aufklärung über Therapie und Wichtigkeit des UV-Schutzes.

Einzeichnen der Felder und Start PDT am

Felder:

Feld 1-

Heute Feld:

Crème und Einwirkungszeit: Metvix 3h

Maschine:

Aktelite

Dosis: 37J/cm^2

Abstand: 6 cm

